	Study 0114 (BPDCN)	Study 0114 (AML)	Study 0214	Study 0314	Total
Capillary leak syndrome	9 (19.1)	10 (20.4)		2 (14.3)	4 (26.7)25 (20.0)
Hypokalemia	10 (21.3)	11 (22.4)		1 (7.1)	3 (20.0)25 (20.0)
Febrile neutropenia	5 (10.6)	17 (34.7)		1 (7.1)	023 (18.4)
Insomnia	7 (14.9)	8 (16.3)		2 (14.3)	6 (40.0)23 (18.4)
Cough	3 (6.4)	13 (26.5)		2 (14.3)	4 (26.7)22 (17.6)
Hypocalcemia	11 (23.4)	8 (16.3)		1 (7.1)	2 (13.3)22 (17.6)
Tachycardia	7 (14.9)	10 (20.4)		2 (14.3)	2 (13.3)21 (16.8)
Pain in extremity	5 (10.6)	8 (16.3)		1 (7.1)	5 (33.3)19 (15.2)
Hyponatremia	9 (19.1)	7 (14.3)		1 (7.1)	1 (6.7)18 (14.4)
Neutropenia	8 (17.0)	7 (14.3)		2 (14.3)	1 (6.7)18 (14.4)
Anxiety	9 (19.1)	4 (8.2)		0	4 (26.7)17 (13.6)

Hypertension	10 (21.3)	5 (10.2)	0	2 (13.3)17 (13.6)
Epistaxis	3 (6.4)	11 (22.4)	1 (7.1)	1 (6.7)16 (12.8)
Blood alkaline phosphatase increased	5 (10.6)	9 (18.4)	1 (7.1)	015 (12.0)
Blood lactate dehydrogenase increased	5 (10.6)	8 (16.3)	2 (14.3)	015 (12.0)
Abdominal pain	4 (8.5)	5 (10.2)	2 (14.3)	3 (20.0)14 (11.2)
Blood creatinine increased	6 (12.8)	6 (12.2)	2 (14.3)	014 (11.2)
Hypoxia	3 (6.4)	6 (12.2)	1 (7.1)	3 (20.0)13 (10.4)
Myalgia	1 (2.1)	8 (16.3)	2 (14.3)	2 (13.3)13 (10.4)

In response to the initial case of Grade 5 CLS, which occurred in a patient with BPDCN treated at the 7 mcg/kg dose level early in the clinical program in Study SL-401-0114, all tagraxofusp protocols were amended to exclude patients with left ventricular ejection fraction (LVEF) below the institutional lower limit of normal, and specify that tagraxofusp infusions should be withheld for patients who have an increase in body weight during the dosing period or other potential early evidence of CLS. After the occurrence of Grade 4 CLS, additional precautions were implemented in all tagraxofusp protocols, including instructions that tagraxofusp dosing cease within a given cycle in the setting of substantial albumin reductions or Grade 3 transaminase elevations. The second Grade 5 case of CLS occurred in a patient with AML treated with tagraxofusp at the 16 mcg/kg dose level, in Study STML-401-0114, a dose level above the MTD determined in that study of 12 m/kg/day.

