6.0 Adverse Events and Reporting Requirements

An adverse event (AE) is the appearance or worsening of any undesirable sign, symptom, or medical condition occurring after starting the study drug even if the event is not considered to be related to study drug. Medical conditions/diseases present before starting study drug are only considered adverse events if they worsen after starting study drug. Abnormal laboratory values or test results constitute adverse events only if they induce clinical signs or symptoms, are considered clinically significant, or require therapy.

The investigator (or physician designee) is responsible for verifying and providing source documentation for all adverse events and assigning the attribution for all adverse events for subjects enrolled.

For the purpose of this study, the investigational component of the treatment plan is tagraxofusp (SL-401). Therefore, serious and unexpected adverse events occurring from the time of infusion of tagraxofusp up to 30 days of the last infusion of tagraxofusp, as defined below, will be reported according to MDACC policy and procedures below. The end of active treatment is the completion of the last infusion of tagraxofusp. Serious adverse events must be followed until clinical recovery and laboratory test have returned to baseline, progression of the event has stabilized, or there has been acceptable resolution of the event.

AEs will graded according to the NCI Common Terminology Criteria for Adverse Events (CTCAE) version 5.0. A copy of CTCAE version 5.0 can be downloaded from the CTEP website https://ctep.cancer.gov/protocolDevelopment/electronic_applications/ctc.htm#ctc_50

Grade – Severity of the adverse event. Grades were developed using the following guidelines:

- Grade 0 – No adverse event or within normal limits
- 1 – Mild adverse event
- 2 – Moderate adverse event
- 3 – Severe adverse event
- 4 – Life-threatening or disabling adverse event
- 5 – Fatal adverse event

Abnormal laboratory values not included in the CTCAE guidelines will be defined per protocol.

Time for AE Collection

Adverse events will be collected from the start of the study drug until 30 days after the last infusion of tagraxofusp.

Adverse Event Reporting

The Investigator or physician designee is responsible for verifying and providing source documentation for all adverse events, and assigning attribution for each event on all subjects enrolled on this study.

Data collection

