6.1 Serious Adverse Event (SAE) Reporting

An adverse event or suspected adverse reaction is considered "serious" if, in the view of either the investigator or the sponsor, it results in any of the following outcomes:

- Death
- A life-threatening adverse drug experience – any adverse experience that places the patient, in the view of the initial reporter, at immediate risk of death from the adverse experience as it occurred. It does not include an adverse experience that, had it occurred in a more severe form, might have caused death.
- Inpatient hospitalization or prolongation of existing hospitalization
- A persistent or significant incapacity or substantial disruption of the ability to conduct normal life functions.
- A congenital anomaly/birth defect.

Important medical events that may not result in death, be life-threatening, or require hospitalization may be considered a serious adverse drug experience when, based upon appropriate medical judgment, they may jeopardize the patient or subject and may require medical or surgical intervention to prevent one of the outcomes listed in this definition.

Examples of such medical events include allergic bronchospasm requiring intensive treatment in an emergency room or at home, blood dyscrasias or convulsions that do not result in inpatient hospitalization, or the development of drug dependency or drug abuse (21 CFR 312.32).

- Important medical events as defined above, may also be considered serious adverse events. Any important medical event can and should be reported as an SAE if deemed appropriate by the Principal Investigator or the IND Sponsor, IND Office.
- All events occurring during the conduct of a protocol and meeting the definition of a SAE must be reported to the IRB in accordance with the timeframes and procedures outlined in "The University of Texas M. D. Anderson Cancer Center Institutional Review Board Policy for Investigators on Reporting Serious Unanticipated Adverse Events for Drugs and Devices". Unless stated otherwise in the protocol, all SAEs, expected or unexpected, must be reported to the IND Office, regardless of attribution (within 5 working days of knowledge of the event).
- All life-threatening or fatal events, that are unexpected, and related to the study drug, must have a written report submitted within 24 hours (next working day) of knowledge of the event to the Safety Project Manager in the IND Office. -

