8.0 Statistical Considerations

Type of study: Open label, single-arm, single center, Phase 2 clinical trial

Number of patients planned: 20

Expected accrual rate: 5-10 patients/year

Toxicity monitoring

Continuous monitoring of toxicity will be performed in all 20 patients. The first 3 patients will be treated with 9 mcg/kg in first 4 cycles. From cycle 5 and beyond in the first 3 patients, the dose will be 12 ug/kg/day. All subsequent patients will be treated with 12 ug/kg/day. Unacceptable toxicities are defined as tagraxofusp-related toxicities which prevent initiation of Cycle 2 of therapy (Any adverse event ³ grade 3 that is both a) considered related to tagraxofusp, and b) does not resolve to \leq grade 2 after a maximum delay of 56-days). Assuming a prior beta distribution of (0.4, 1.6), corresponding to an unacceptable toxicity rate of 30%, treatment will terminate if the $Pr(dt > 0.20 | \text{data}) > 0.95$, where dt is the toxicity rate attributable to the tagraxofusp treatment. The decision rule for terminating for toxicity is presented in Table 4 and the software used for this Bayesian toxicity monitoring rule is Multc Lean version 2.1.0. The operating characteristics for this rule are presented in Table 5. The method used to produce the decision rule and operating characteristics was designed by Thall, Simon, and Estey ^{26, 27} and extended by Thall and Sung. ²⁸

Table 4 Stopping criteria

Total Patients Enrolled	Stopping Condition (# of patients experiencing unacceptable toxicities)
3-4	3-4
5-8	4-8
9-11	5-11
12-14	6-14
15-18	7-18
19	8-19
20	Patient enrollment ends

Table 5 Operating characteristics

True % of DLTs	Pr (stopping early)	Average # of patients treated
0.05	0.00	20
0.10	0.01	20
0.20	0.11	19
0.30	0.38	16
0.40	0.70	12
0.50	0.91	9

Analysis

Demographic and baseline characteristics will be summarized. Categorical measures will be summarized using frequencies and percentages while continuous variables will be summarized using mean, standard deviation, median, minimum, and maximum.

The primary endpoint of the study is the tolerability of tagraxofusp post-SCT, where tolerability is defined as receipt of at least 75% of planned tagraxofusp doses in at least 4 cycles of therapy. The following table shows the exact 95% confidence intervals for different percentages of patients, out of 20 patients, experiencing tolerability:

Patients experiencing tolerability		95% Exact
Number	Percentage	Confidence Interval
2	10%	1.2% - 31.7%

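### At 2 toxicities in the first 2 patients, the stopping formula in Section 8.0 is met, but Table 4 starts at 3 patients and does not call for a stop

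*Combined protocol and SAP*

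**What the plan says.** All of the following is in Section 8.0.

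- **Monitoring:** "Continuous monitoring of toxicity will be performed in all 20 patients". No first look or minimum sample size is given.
- **Event counted:** "Unacceptable toxicities are defined as tagraxofusp-related toxicities which prevent initiation of Cycle 2 of therapy". The text explains this as a drug-related event of Grade 3 or higher that has not come down to Grade 2 or lower after a delay of up to 56 days.
- **Formula:** under a Beta(0.4, 1.6) prior, treatment ends when Pr(toxicity rate > 0.20 given the data) is above 0.95.
- **Table 4:** this is named as the decision rule. Its second column is headed "Stopping Condition (# of patients experiencing unacceptable toxicities)", and its first row covers 3-4 patients, with stopping at 3 or more events. Nothing is printed for 1 or 2 patients.
- **Table 5:** the probability of stopping early is 0.00, 0.01, 0.11, 0.38, 0.70 and 0.91 at true rates of 0.05, 0.10, 0.20, 0.30, 0.40 and 0.50. The average numbers treated are 20, 20, 19, 16, 12 and 9.
- **Summary Reports:** the first toxicity report is due once 3 evaluable patients have completed a cycle, and later ones every 2-3 evaluable patients.

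**The concern.** The formula and the table are meant to be one rule in two forms. If they differ at any count that can occur, staff reading the text and staff reading the table would act differently on the same data. The count in question is the worst possible start: both of the first two patients have an unacceptable toxicity. Under the text, treatment ends before a third patient is treated. Under the table, a third patient is treated. If that patient has no event, accrual continues with no record that the formula had been crossed. Safety is the primary objective and this is the only numeric trial-level stopping rule in the plan, so it should be unambiguous from the first patient.

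**Working it through.** **Inputs (Section 8.0).** Prior Beta(0.4, 1.6), reference rate 0.20, cut-off 0.95, maximum 20 patients.

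**Formula.** After x events in n patients the posterior is Beta(0.4 + x, 1.6 + n − x). The boundary at n is the smallest x for which Pr(rate > 0.20) is above 0.95.

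**Step 1: reproduce Table 4.** The formula returns every printed boundary from n = 3 to n = 19. Some values on either side of the boundary:

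| n | Just below the boundary | At the boundary |
|---|---|---|
| 3 | 2 events: 0.907 | 3 events: 0.990 |
| 4 | 2 events: 0.846 | 3 events: 0.973 |
| 5 | 3 events: 0.948 | 4 events: 0.993 |
| 18 | 6 events: 0.883 | 7 events: 0.955 |
| 19 | 7 events: 0.9405 | 8 events: 0.979 |

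**Step 2: apply the same formula below n = 3.**

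- 1 of 1: Beta(1.4, 1.6), probability 0.824. No stop.
- 2 of 2: Beta(2.4, 1.6), probability 0.957. **Stop.**
- 2 of 3, if the third patient has no event: Beta(2.4, 2.6), probability 0.907. No stop.

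The formula therefore implies exactly one row that Table 4 does not print: 2 patients, 2 events.

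**Step 3: find which version Table 5 describes.** An exact patient-by-patient binomial recursion, with the last look at n = 19, gives:

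| True rate | Pr(stop), looks from n = 3 | Average N | Pr(stop), with 2 of 2 added | Average N |
|---|---|---|---|---|
| 0.05 | 0.001 | 19.99 | 0.003 | 19.95 |
| 0.10 | 0.009 | 19.88 | 0.017 | 19.74 |
| 0.20 | 0.108 | 18.80 | 0.127 | 18.39 |
| 0.30 | 0.376 | 16.01 | 0.395 | 15.41 |
| 0.40 | 0.701 | 12.19 | 0.712 | 11.51 |
| 0.50 | 0.910 | 8.73 | 0.914 | 8.04 |

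The left-hand pair rounds to Table 5 throughout. The right-hand pair does not: at 0.20 it would print 0.13 rather than 0.11. Table 5 was therefore computed with a first look at patient 3.

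**Step 4: size when the pattern occurs.** Two events in the first two patients have probability p². At a true rate of 0.30 that is 0.09. The whole difference in average N comes from those trials, so under Table 4 they treat on average (16.01 − 15.41)/0.09, or about 6.7, more patients than under the formula. At 0.20 the figure is (18.80 − 18.39)/0.04, or about 10.

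**Step 5: sensitivity to the prior.** Beta(0.4, 1.6) has mean 0.4/2.0 = 0.20, although the text attaches 30% to it. That is a separate slip. With Beta(0.6, 1.4), whose mean is 0.30, 2 of 2 gives 0.974, so the disagreement does not depend on it. Only Beta(0.4, 1.6) reproduces all of Table 4.

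**The case against.** The best defence is that three patients was plainly the intended first look. The text names Table 4 as the decision rule, the table starts at 3, the first summary report follows 3 evaluable patients, three is the size of the group started at the lower dose, and Table 5 was computed that way. All of this stands as an explanation of the missing row. It does not remove the disagreement, because a reporting date does not amend a termination formula that carries no minimum and sits beside a statement of continuous monitoring.

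It is also true that the extra row does little on average, and that at a true rate of 0.10 it nearly doubles early stopping, from 0.009 to 0.017.

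Three stronger readings are tempting, and the documents do not support them.

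- **A reader might infer that 2 deaths in 2 patients, or 6 in 18, could not stop the trial.** Table 4 merely does not mandate a stop. Under Section 6.1 all serious adverse events go to the IND Office within 5 working days whatever their attribution. They are also reported to the IRB under its policy and forwarded to FDA under the regulations, and any of these bodies can act. At 6 of 18 the formula (0.883) and the table agree, so that example shows no inconsistency.
- **A reader might infer that Table 4 is demonstrably too loose for deaths**, because it stops with probability only 0.01 or 0.11 at related death rates of 10% or 20%. Those figures assume that deaths are the only qualifying events and that all of them precede Cycle 2. The plan pools deaths with other toxicities and sets no tolerable death rate to compare with. A separate boundary for deaths is a design preference.
- **A reader might infer that fatal capillary leak syndrome escapes the 24-hour report.** Section 2.3.2 describes fatal cases, and Section 6.1 limits that report to unexpected related events. Whether such a death would be classed as expected is a judgement that the documents do not settle.

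**Conclusion.** The point holds as an inconsistency between the stated formula and the printed rule at one count, 2 of 2, where the posterior probability is 0.957 against a cut-off of 0.95. It rests only on the prior, reference rate and cut-off in Section 8.0, and on the absence of any stated minimum. The effect on operating characteristics is small: the probability of early stopping changes by at most about 0.02 at any rate in Table 5. It matters more in the rare trial that starts this way, where text and table give opposite instructions about the third patient.

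A secondary point is for the sponsor to consider and is not an error. Section 6.0 grades a fatal event as 5, so a related death in Cycle 1 falls within Grade 3 or higher and counts once, the same as an unresolved Grade 3 event. Because the counted event is tied to starting Cycle 2, a related death in Cycle 2 or later may not count at all, although Section 4.2 allows 24 cycles or more.

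**What to change.** Reconcile the text and Table 4 in one of two ways.

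1. **Preferred: add the row "2 patients: 2" to Table 4 and recompute Table 5.** The stated formula then holds without exception. At true rates of 0.05, 0.10, 0.20, 0.30, 0.40 and 0.50, the probability of stopping early becomes 0.003, 0.017, 0.127, 0.395, 0.712 and 0.914, and average N becomes 19.9, 19.7, 18.4, 15.4, 11.5 and 8.0. The cost is one row, a recomputed table, and the rise in early stopping at a true rate of 0.10 from 0.009 to 0.017.
2. **Alternative: state that the formula is applied only from patient 3.** Tables 4 and 5 then stand as printed. The cost is one sentence, plus an open acceptance that 2 of 2 does not end treatment although the posterior exceeds the cut-off.

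Separately, add a sentence saying how related deaths enter trial-level monitoring, including those in Cycle 2 or later. Any threshold is for the sponsor to set.
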